6 Imaging on-study will be performed every 9 weeks (± 5 days) after the first dose of study treatment for the first 18 months then every 12 weeks thereafter. On-study imaging should follow calendar days and not be adjusted for delays in cycle starts or extension of treatment cycles due to toxicity. The same imaging technique should be used in a subject throughout the study.

7 Per the RECIST v1.1 and irRC, if imaging shows progressive disease, the imaging assessment should be performed at a minimum of 4 weeks later to confirm progression as described.

8 For patients that discontinue treatment for reasons other than disease progression, every effort should be made to continue monitoring their disease status by radiographic imaging at the imaging interval that was used at the time they came off study until 1) start of new anti-cancer therapy, 2) documented disease progression, 3) death, or 4) end of study, whichever occurs first.

9 If a prior scan was obtained within 4 weeks before the date of discontinuation, then a scan at the discontinuation visit is not required. In subjects who discontinue study drug without confirmed disease progression, a radiological evaluation should be repeated at the time of treatment discontinuation (i.e., date of discontinuation ± 4 week window).

10 If labs at screening are collected within 7 days of Cycle 1 Day 1, these do not need to be repeated at this visit.

11 Pre-dose laboratory results need to be within 2 days of dosing at all cycles.

12 See Table 2 for complete listing of all required laboratory tests required.

	Screening	Treatment Phase 				EOT	Post-Treatment	
		C1D1	C2D1	C3D1	Day 1 All Subsequent Cycles	Discontinuation Visit	Follow-Up Visits	Survival Follow-Up
Evaluation/Window	Day -28 to Day -1	Day 1	± 3 Days	± 3 Days	± 3 Days	+ 5 Days	Every 9 Weeks After Discontinuation (± 7 Days)	Every 12 Weeks (± 7 Days)
Hematology with differential	X	X	X	X	X	X	X	
Lipid panel	X	X	X	X	X	X		
Coagulation panel (PT, aPTT, INR) 	X							
Endocrine function testing 	X	X	X	X	X		X	
Serum pregnancy test or urine 	X							
Tumor Markers 		X	X	X	X	X		
Urinalysis	X	X	X	X	X	X		
Required research samples (blood)		X 	X	X	X			
TUMOR BIOPSY/ARCHIVAL TISSUE COLLECTION								
Fresh tissue collection for Correlative studies (tissue) 	X			X				

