**Table 8: Response Evaluations based on Endpoints**

	Progression Free Survival (PFS)	Response Rate (RR)	Overall Survival (OS)	Safety
Primary or Secondary	Primary	Secondary	Secondary	Secondary
Definition and Time Frame	Time from first treatment to documented disease progression or death due to any cause	Defined as proportion of patients with RECIST v1.1 response (sum of partial and complete responses).	Time from first treatment until the day of death due to any cause	Assessed on the basis of adverse events (AEs; graded according to the National Cancer Institute Common Terminology Criteria for Adverse Events, version 4.03)
Safety Issue (Yes/No)	No	No	No	Yes
Relevant Subset	Patients who receive baseline imaging and at least first follow-up imaging at 9 weeks.	Patients who receive baseline imaging and at least first follow-up imaging at 9 weeks.	All enrolled patients	Patients who receive at least 1 dose of pembrolizumab.
Measurement Method	CT or MRI every 9 weeks	CT or MRI every 9 weeks	CT or MRI every 9 weeks	CTCAE v5
Measurement Time Points	Every 9 weeks	Every 9 weeks	Every 9 weeks	Day 1 of each cycle

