## 12. STATISTICS CONSIDERATIONS

### 12.1. Statistical Design

This is a single-stage study for the doublet epacadostat and pembrolizumab. A 6-month PFS of 20% was observed using single agent pembrolizumab and is the basis for the null hypothesis of the present study (Bang, abstract 4001, GI ASCO 2015). We will enroll 30 patients over 18 months and follow patients for at least 6 months. This design has 80% power to reject a 20% PFS rate, if the true PFS is 39%. Calculation based on binomial probabilities with a one-sided significance of 10%. The level of significance for the primary endpoint in Phase 2 is one-sided 10%, which is deemed acceptable for a proof-of-concept study.

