## 12.2. Safety Analyses

### 12.2.1. Analysis Plan

The analysis will be done on the intent to treat population and patients who drop out will be censored at the point of last follow up.

The primary endpoint of the study is 6-month Progression-free survival (PFS), which is defined as number of days from the first day of taking study dose to the earlier of death or disease progression by RECIST v1.1 for solid tumors. Median PFS will be estimated using the Kaplan-Meier method.

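### Table 8 and Section 12.2.1 name different populations for the primary PFS endpoint, and the Table 8 population drops early deaths and so overstates 6-month PFS

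*Combined protocol and SAP*

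**What the plan says.** Table 8 in Section 10.4 labels PFS as the primary endpoint and gives its relevant subset as "Patients who receive baseline imaging and at least first follow-up imaging at 9 weeks". The same column defines PFS as "Time from first treatment to documented disease progression or death due to any cause".

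Section 12.2.1 states "The analysis will be done on the intent to treat population", without defining that population, and adds that "patients who drop out will be censored at the point of last follow up". Its next paragraph names 6-month PFS as the primary endpoint, "defined as number of days from the first day of taking study dose to the earlier of death or disease progression by RECIST v1.1". These sentences sit under the heading for safety analyses (12.2), but what they describe is the primary efficacy endpoint, and Table 8 gives safety its own population (at least one pembrolizumab dose).

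Section 12.1 sizes the trial on 30 patients with a one-sided 10% binomial test of 20% against 39%. It gives no cut-off count.

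For OS, Table 8 says "All enrolled patients", while Section 12.3 places the secondary efficacy analyses, OS among them, in an efficacy evaluable population.

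**The concern.** Two sections give two denominators for the primary endpoint, and nothing ranks them. The Table 8 version selects on outcome. A patient who dies before any follow-up scan is a PFS event by Table 8's own definition and a certain failure at 6 months, yet is outside the subset. Removing only failures raises the observed rate, and a single-arm trial has no control group in which the same exclusion would offset it.

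Patients who progress early are in an unclear position. Section 10.2.1 allows extra assessments when progression is suspected, and note 9 to the Schedule of Events says that, for patients stopping study drug without confirmed progression, "a radiological evaluation should be repeated at the time of treatment discontinuation". Table 8 does not say whether such a scan satisfies its 9-week condition.

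With neither the denominator nor the cut-off count fixed, both could be settled after the data are seen.

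**Working it through.** **Inputs.** From Section 12.1: n = 30, null rate 0.20, alternative 0.39, one-sided 0.10, binomial. The share of patients who die before any follow-up scan is not in the documents. It is treated as an assumption, x = 5%, 10% and 20%.

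**1. The plan's own figure.** The cut-off is the smallest r with P(X ≥ r | n, 0.20) ≤ 0.10.

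- n = 30, r = 9: P = 0.129, too large.
- n = 30, r = 10: P = 0.061. Power = P(X ≥ 10 | 30, 0.39) = 0.793.

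This reproduces the stated 80% power, so the design was sized on all 30 patients and not on an imaged subset.

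**2. Effect on the estimate.** If a share x is excluded and all of them are failures, the apparent rate is 0.20/(1 − x):

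- 0.20/0.95 = 21.1%
- 0.20/0.90 = 22.2%
- 0.20/0.80 = 25.0%

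**3. Effect on the test if the cut-off is re-derived for the evaluable number.** The same rule gives r = 10 for n = 30 and 29, r = 9 for n = 28 to 25, and r = 8 for n = 24. Take 9 patients progression-free at 6 months:

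| Early deaths removed | Result | P(X ≥ 9 given 0.20) | Decision |
|---|---|---|---|
| 0 | 9/30 = 30.0% | 0.129 | fails |
| 1 | 9/29 = 31.0% | 0.108 | fails |
| 2 | 9/28 = 32.1% | 0.090 | passes |

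With 2 to 5 removed, only a count of exactly 9 changes the decision. A count of 8 needs 6 removed: 8/25 gives 0.109 and fails, 8/24 gives 0.089 and passes.

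For type I error, let the evaluable number m follow Bin(30, 1 − x), re-derive r for each m, and average P(X ≥ r | m, 0.20/(1 − x)) over m:

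| x | Type I error |
|---|---|
| 5% | 0.087 |
| 10% | 0.118 |
| 20% | 0.187 |

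It equals 0.10 at x = 7.0%, which is about 2 of 30 patients.

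**4. Effect on the test if the cut-off stays at 10.** Removing failures does not change the number of successes, so P(at least 10 successes) remains 0.061 for every x. Only the reported rate is inflated.

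**5. Plausible size of x.** Section 2.1 quotes 6-month OS of 66% in the pembrolizumab gastric cohort and median OS of 3 to 5 months in second-line trials. Assuming a constant hazard, with 9 weeks = 63/30.44 = 2.07 months:

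- 1 − 0.66^(2.07/6) = 13% dead by week 9
- 1 − 0.5^(2.07/5) = 25%
- 1 − 0.5^(2.07/3) = 38%

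Eligibility (ECOG 0 or 1, life expectancy of at least 12 weeks) points to the low end or below. Some of these deaths may also follow an early scan, and the constant hazard is itself an assumption.

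**6. What Section 12.2.1 leaves open.** Suppose 2 of 30 patients drop out and are censored before the first event, and 9 of the remaining 28 are progression-free at 6 months. A Kaplan-Meier estimate at 6 months is then 9/28 = 32.1%, against 9/30 = 30.0% if the two count as not progression-free. If they left because they were deteriorating, the higher figure is biased upward. The plan assigns Kaplan-Meier only to median PFS, so this is an illustration. A binomial test has no censored category, and the plan does not say how such patients enter it.

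**The case against.** The best reply is that intent to treat is the natural reading. Section 12.3 reserves the efficacy evaluable set for secondary efficacy, which implies that the primary endpoint is analysed otherwise. Section 12.1 powers on 30. Table 8 has visible drafting slips: it measures OS by CT or MRI, and its safety column cites two CTCAE versions. On this view one table cell needs correcting. Against it, Table 8 explicitly gives PFS a narrower population than OS, the intent-to-treat sentence is itself undefined and sits under a safety heading, and nothing tells an analyst to disregard the table. The reply shows which text should be kept. It does not remove the conflict.

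A second reply is that the decision changes only under several conditions: Table 8 is applied, the cut-off is re-derived, at least 2 of 30 are excluded, and the count falls at the margin. That is correct and limits the claim about the test. It does not touch the inflation of the estimate, which follows as soon as one early death is dropped.

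A third is that counting dropouts as failures is a separate missing-data choice and has a price. That is fair. The population conflict can be resolved without it, although the binomial test still needs some rule for these patients.

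**Conclusion.** The concern holds and should be corrected before analysis. The two sections conflict, and Table 8 conflicts with its own event definition. Applying Table 8 can only raise 6-month PFS: a true 20% would read as 21.1% to 25.0% with an assumed 5% to 20% of patients dying before any follow-up scan. The effect on the test is conditional. With the cut-off re-derived, type I error runs from 0.087 to 0.187 over that range and exceeds 0.10 only above about 7% excluded. With the cut-off held at 10 it stays at 0.061. The excluded share is an assumption throughout. The direction of the bias is not, because every patient removed by early death is a failure.

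**What to change.** - **Population.** Replace the PFS subset in Table 8 with the population used in Section 12.2.1, and define it once. All patients who received at least one dose of study treatment fits the PFS start date. All enrolled patients would also resolve the conflict. If the treated set is chosen, say that it is the definition adopted and report how many enrolled patients were never dosed.
- **Events.** State that death before the first follow-up scan, and progression documented on any earlier scan, are PFS events.
- **Patients without a scan or event.** For the 6-month binomial test, count treated patients who leave without either as not progression-free. Keep the Section 12.2.1 censoring for the Kaplan-Meier analysis. Name the binomial proportion as the headline 6-month figure, since the two can differ.
- **Cut-off.** State the count and the n it applies to; with all 30 analysed this is at least 10 of 30.
- **Sensitivity.** Keep the week-9-imaged subset as a labelled sensitivity analysis.
- **OS.** Use the same population in Table 8 and Section 12.3.

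The cost is wording in Table 8 and Sections 12.1, 12.2.1 and 12.3, with no extra patients or visits. Reported 6-month PFS may be slightly lower. The dropout rule is conservative: if an assumed 5% leave without an event for reasons unrelated to outcome, the effective rate at the alternative is 0.39 × 0.95 = 0.3705, and power with at least 10 of 30 falls from 0.793 to 0.725. The plan should acknowledge that if the rule is adopted.

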### **1.2. Secondary Objectives**

- 1.2.1. To evaluate objective response rate (RR) by RECIST v1.1 and irRC
- 1.2.2. To evaluate overall survival (OS)
- 1.2.3. To assess the safety and tolerability of epacadostat in combination with pembrolizumab by NCI CTCAE v5

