###### **4.4.2.1. Epacadostat (INCB024360)**

Site staff will dispense medication sufficient for a 3-week cycle (21 days). Subjects will be administered study drug at 300 mg oral, twice daily, continuous dosing. All twice daily doses of epacadostat will be taken orally in the morning and evening, approximately 12 hours apart without regard to food. If the morning or evening dose is missed by more than 4 hours, that dose should be skipped and the next scheduled dose should be taken at the usual scheduled time. Doses of epacadostat will be self-administered except on the day of the cycle that the patient is visiting the study clinic for infusion (Day 1 of each cycle); epacadostat will be taken prior to pembrolizumab infusion.

Epacadostat compliance will be calculated based on the drug accountability documented and monitored by the site staff (tablet counts and pill diary). The objective is 100% compliance and investigators and their staff should evaluate compliance at each visit, and take appropriate steps to optimize compliance. If the subject falls below 85% compliance, based on 2 subsequent visits,

then it will need to be addressed immediately, and could be means to remove the subject from the study.

Epacadostat will be given daily in combination with pembrolizumab every 3 weeks for up to 24 months provided subjects are receiving benefit from treatment and have not had disease progression or met any criteria for study withdrawal. Intrasubject escalation of epacadostat is not permitted. Single agent epacadostat may be continued beyond 24 months provided the patient has benefit.

Subjects will receive treatment in continuous 21 day cycles; however, treatment may include temporary interruptions to allow for resolution of certain toxicities. Interruptions from the protocol-specified treatment plan for > 12 weeks between epacadostat and pembrolizumab doses due to toxicity require consultation between Merck/Incyte and the investigator and written documentation of the collaborative decision on subject management.

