## **7. ADVERSE EVENTS AND REPORTING PROCEDURES**

### **7.1. Adverse Event Definition and Reporting**

An AE is defined as any untoward medical occurrence in a patient or clinical investigation subject administered a pharmaceutical product and which does not necessarily have to have a causal relationship with this treatment. An adverse event can therefore be any unfavorable and unintended sign (including an abnormal laboratory finding, for example), symptom, or disease temporally associated with the use of a medicinal product or protocol-specified procedure, whether or not considered related to the medicinal product or protocol-specified procedure. Any worsening (i.e., any clinically significant adverse change in frequency and/or intensity) of a preexisting condition that is temporally associated with the use of the Merck's product, is also an AE.

AEs can be spontaneously reported or elicited during open-ended questioning, examination, or evaluation of a subject. In order to prevent reporting bias, subjects should not be questioned regarding the specific occurrence of one or more AEs.

AEs will be graded according to NCI CTCAE v5. Both serious and non-serious AEs will be clearly noted in source documentation and listed on study specific eCRFs. The investigator or designee will assess each AE to determine whether it is unexpected according to the informed consent document, protocol document, or IBs, and related to the investigation. After the end of treatment, each subject will be followed up to 30 days or until new anti-cancer treatment is initiated, whichever occurs first for adverse event monitoring, including SAEs grade 3 and above, and all subsequent follow-up reports will be reported to the

Stanford Cancer Institute Data and Safety Monitoring Committee (DSMC) using the study specific eCRF regardless of the event's relatedness to the investigation. Events meeting the IRB definition of 'Unanticipated Problem' will be reported to the IRB within 10 working days of investigator determination expedited reporting is required, or within 5 working days for deaths or life-threatening experiences.

Changes resulting from normal growth and development that do not vary significantly in frequency or severity from expected levels are not to be considered AEs. Examples of this may include, but are not limited to, teething, typical crying in infants and children and onset of menses or menopause occurring at a physiologically appropriate time.

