## **7.8. Evaluating Adverse Events**

All investigators who are qualified physicians and delegated, can evaluate for AEs. All AEs will be graded based on the NCI CTCAE v.5. Any AE which changes in grade over the course of a given episode will have each change of grade recorded independently in the appropriate eCRF. All adverse events regardless of grade must be evaluated for seriousness and causality to the investigational agents. See Table 6 for further guidance on evaluating an AE by grade, seriousness, and causality.

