### 12.3. Secondary Analyses

Secondary efficacy analysis will be conducted for the efficacy evaluable population. Secondary endpoints and analyses are as follows:

To evaluate response rate (RR). Response will be determined by RECIST v1.1 for solid tumors. The 95% exact CI for the RR will be estimated using the Clopper-Pearson method. For objective responders, the duration of response is the time from the first objective response contributing to an objective response, to the first objective response of PD (by RECIST v1.1) occurring after the first objective response contributing to the objective response.

To evaluate overall survival (OS). Time-to-event data will be analyzed by the Kaplan-Meier method, treating subjects with no observed death or progression as censored at their last date known to be alive. For the OS analysis, the nonparametric Kaplan-Meier method will be used to estimate the survival time distribution and the median survival.

To assess the safety and tolerability of epacadostat in combination with pembrolizumab. AEs will be coded by the MedDRA, and incidences will be tabulated by preferred term and system organ class for all events, related events, and events  $\geq$  Grade 3. Severity of AEs will be based on the CTCAE v5 scale as indicated. Quantitative safety variables and their changes from baseline (laboratory, vital signs) will be summarized with descriptive statistics. Clinically significant abnormal values will be flagged and tabulated based on predefined criteria. Exposure will be analyzed by describing dose intensity, which is defined as the dose-received divided by the dose planned over a given time interval. This will be done by cycle as well as overall cycles received for epacadostat and pembrolizumab. For each cycle, incidences of dose reductions and cycle

delays will also be tabulated, by reason for the reduction or delay. The percentage of subjects with any delay and/or reduction will also be calculated.

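### Table 8 ties the safety population to pembrolizumab alone, unreconciled with Section 12, and Tables 6 and 8 still cite CTCAE v4.03 where the rest of the plan uses v5

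*Combined protocol and SAP*

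**What the plan says.** **Population.** In Section 10.4, Table 8, the relevant subset for safety is "Patients who receive at least 1 dose of pembrolizumab". Epacadostat exposure is not mentioned. Section 1.2 sets the objective: "To assess the safety and tolerability of epacadostat in combination with pembrolizumab by NCI CTCAE v5". Section 4.4.2.1 fixes the order on infusion days: "epacadostat will be taken prior to pembrolizumab infusion".

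Section 12.2 is headed as the safety analyses. Its only subsection, 12.2.1, names the intent-to-treat population, but the text there concerns progression-free survival (PFS). Section 12.3 assigns an efficacy-evaluable set to the secondary efficacy analyses. It then describes adverse event tables and dose intensity for both drugs without saying which patients they cover.

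**Grading version.** Table 8's definition row for safety cites "National Cancer Institute Common Terminology Criteria for Adverse Events, version 4.03". The measurement-method row of the same column says v5. Section 12.3 states: "Severity of AEs will be based on the CTCAE v5 scale as indicated". Section 7.1 has "AEs will be graded according to NCI CTCAE v5" and Section 7.8 has "All AEs will be graded based on the NCI CTCAE v.5". Table 6, to which Section 7.8 sends investigators for guidance, labels its grade block V4.03.

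**The concern.** The safety question is how well patients tolerate epacadostat added to pembrolizumab. A safety set is normally built on exposure to any study treatment, so that no one who took a drug and had an event is left out of the tables. Table 8 builds it on exposure to one of the two drugs, and not the one under test. Epacadostat toxicity is a live question at this dose. Section 2.2.4 reports that 6 of 15 patients at 300 mg twice daily interrupted epacadostat for adverse events in the earlier combination study, against 1 patient at 100 mg twice daily.

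What is at stake is the denominator of every safety percentage, and whether an event after epacadostat alone is counted. On grading, Section 12.3 tabulates events of Grade 3 and above, so the version needs to be the same wherever it is named.

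**Working it through.** The plan gives no figure on this point to reproduce. The 80% power in Section 12.1 concerns 6-month PFS and uses none of the inputs below.

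**1. Can a patient take epacadostat only?** Both drugs start on Cycle 1 Day 1 (Section 4.4.1 and the calendar in Section 9), with epacadostat first (Section 4.4.2.1). So it is possible, but only if a patient takes a Day 1 oral dose and then receives neither that infusion nor any later one. Patients who stay on single-agent epacadostat after 24 months (Sections 4.2 and 4.4) have already had pembrolizumab and remain in the subset.

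**2. Would the event be captured?** Yes. Section 4.9.1.1 monitors adverse events from the start of treatment and records them whatever their cause. Sections 7.1 and 7.5.1 start serious-event reporting to the epacadostat manufacturer on the day treatment starts. The loss would be from the safety endpoint, not from the database.

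**3. Which population applies?**
- Table 8: given pembrolizumab at least once.
- Section 12.2.1: intent to treat, under a safety heading but in text about PFS.
- Section 12.3: none stated for safety.

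No passage says which of these governs.

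**4. Size per patient.** Inputs: N = 30 (Sections 12.1 and 12.4). Two quantities are assumptions, because the documents give neither: one epacadostat-only patient, and e patients with a given event among the other 29.

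- The excluded patient had the event. The rate in all dosed patients is (e + 1)/30 and the Table 8 rate is e/29. The difference is (e + 1)/30 − e/29 = (29 − e)/870.
  - e = 0: 1/30 − 0/29 = 3.3 points, the maximum.
  - e = 6: 7/30 − 6/29 = 23.3% − 20.7% = 2.6 points.
- The excluded patient did not have the event. The all-dosed rate is e/30 and the Table 8 rate is e/29, so exclusion raises the rate by e/870.
  - e = 6: 20.0% becomes 20.7%, up 0.7 points.

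Range for k epacadostat-only patients, assuming all k had the event and 6 others did:

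| k | Table 8 rate | All dosed patients |
|---|---|---|
| 0 | 6/30 = 20.0% | 6/30 = 20.0% |
| 1 | 6/29 = 20.7% | 7/30 = 23.3% |
| 2 | 6/28 = 21.4% | 8/30 = 26.7% |
| 3 | 6/27 = 22.2% | 9/30 = 30.0% |

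**5. Grading version, side by side.**
- v4.03: Table 8 definition row; Table 6 label.
- v5: Table 8 method row; synopsis; Sections 1.2, 4.9.1.1, 7.1, 7.8, 7.9 and 12.3.

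Table 8 therefore disagrees with itself within one column, and the Table 6 label disagrees with the text that introduces the table.

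**The case against.** The strongest reply on population is that the group may be empty. Both drugs start on the same day at a supervised visit, and the protocol gives no reason to expect many patients to swallow the first dose and miss every infusion. That stands, so no claim can be made that patients will actually be lost. It can also be said that a patient never infused did not receive the combination named in the objective, so Table 8's rule is not plainly wrong. That has some force, but such a patient did receive study treatment under this protocol. Section 12.3 also plans exposure summaries for both drugs and sets no pembrolizumab condition.

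A reader might infer that the rule can only remove toxicity, and so always flatters the regimen. It does not. Exclusion shrinks the denominator too, so the rate of any event the excluded patient did not have goes up. A reader might also take 3.3 points as the cost of each excluded patient. It is the ceiling, reached only when nobody else has the event.

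On grading, the reply is that v4.03 is leftover text: Section 12.3 governs the tabulation and says v5, and Table 6 prints only general grade descriptions. That is persuasive. A reader might infer that the plan will yield two competing tabulations of Grade 3 and above. The documents do not support this, and they do not show which events would grade differently under the two versions.

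**Conclusion.** The point holds as a minor one. Table 8 states a safety population that omits anyone exposed to epacadostat alone, and Section 12 neither confirms nor replaces it, so the population is unreconciled. This is not a demonstrated loss of safety data: events are still collected, and the number of patients affected is unknown and may be zero. If one patient is affected, the reported rate of an event that patient had falls by between 0 and 3.3 points in 30, depending on how many others had it. Rates of events that patient did not have rise slightly. These figures assume all 30 enrolled patients take at least one dose of a study drug.

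The CTCAE conflict is a plain textual contradiction, with v5 clearly the prevailing version. No numerical effect is claimed for it. Neither matter touches the primary endpoint or its power.

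**What to change.** - In Table 8 and Section 12.3, define the safety population as all patients who receive at least one dose of either study drug.
- In Section 12.2.1, say that intent to treat refers to the PFS analysis, or move that text out from under the safety heading.
- Replace v4.03 with v5 in Table 8's definition row and in the Table 6 label.

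The cost is a few text edits, best made before the safety tables are produced. Data collection, sample size, treatment and the primary analysis do not change. If no patient turns out to have taken epacadostat alone, the results are the same as under Table 8's rule.
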